Ruminococcaceae. In our published experience, a single enema from a rationallyderived donor was associated with significantly lower total and HE-related hospitalizations compared to patients who were randomized to standard of care, with a stable long-term course over >1 year¹⁰. Our data show that FMT was associated with favorable changes in fecal bile acid (BA) profile with a decrease in proportions of fecal secondary BAs, conjugated BAs and increase in sulfated BAs, indicating a healthier milieu. We also have preliminary data defining the safety of oral FMT capsules in patients with cirrhosis and HE in a current trial led by us¹¹. The use of combined oral *and rectal routes of FMT, which can potentially alleviate both small bowel and colonic translocation are likely to be better than either alone*.

Details of the team's experience with FMT in cirrhosis using enema¹⁰:

In the trial conducted by us under IND 16452, we have recruited 20 subjects with cirrhosis and recurrent HE (the same population proposed for this trial). All subjects completed the 5-month follow-up without SAEs that were associated with FMT. The baseline subject characteristics are:

	No-FMT group	FMT group	P value
	(n=10)	(n=10)	
Age	62.9±9.8	64.5±5.1	0.65
Gender (Men/Women)	10/0	10/0	1.0
Race (Caucasian, African- American, Hispanic, others)	6/3/1/0	7/2/1/0	0.9
MELD score	13.2±3.7	12.0±2.9	0.36

None of the subjects reached a grade of 3 or change in >2 of any of their GI symptoms throughout the study. Similarly, none of the subjects developed clinically relevant hepatic encephalopathy or significant changes in liver chemistries or labs (WBC

>12,000 or <1000/ml, MELD >8 increase, AST/ALT/ALK>10 times ULN). As shown in the table below, there was a significant improvement (reduction in the MELD score) in the FMT group compared to the no-FMT group at day 1 post-FMT (day 6) and day 30 post-FMT (day 35) compared to baseline. No changes in the WBC count were observed.

	No-FMT group	FMT group	P value
	(n=10)	(n=10)	
MELD score			
Day 0 minus day 6	0.6±1.4	-1.5±1.4	0.004
Day 0 minus day 12	0.4±1.3	-0.2±1.3	0.3
Day 0 minus day 35	1.2±2.4	-0.9±1.7	0.04
Serum WBC count			
Day 0 minus day 6	-0.1±0.6	0.1±1.2	0.60
Day 0 minus day 12	-0.53±0.9	0.2±1.0	0.10
Day 0 minus day 35	0.22±0.5	0.2±0.9	0.95

There was a significant reduction in hospitalizations and improvement in brain function in patients randomized to FMT+ antibiotics compared to those randomized to SOC¹⁰.

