The primary aim is: To evaluate the safety and tolerability of fecal transplant through rectal and oral capsular routes in cirrhosis and HE from a liver disease and symptom standpoint using analysis of serious adverse events, especially HE recurrence, in a placebo-controlled trial.

Secondary aims are between the groups:

- 1. Safety and tolerability of FMT compared to placebo
 - a. Frequency, severity and relatedness of solicited and unsolicited AEs through day 30
 - b. Occurrence of new potentially transmitted infections through six-months post FMT
 - c. Occurrence of new onset or significant worsening of chronic medical conditions post-FMT
- 2. To define the changes in microbiota composition and function of the stool microbiota after FMT compared to pre-FMT baseline and donor compared to placebo

- 3. To evaluate changes in systemic inflammatory cytokines and endotoxin, quality of life and cognitive function compared to pre-FMT baseline and compared to placebo
- 4. To determine occurrence of new onset or significant worsening of chronic medical conditions through six months post-FMT and compared to placebo
- 5. To evaluate the changes in the microbiota after the second oral FMT vs. placebo compared to baseline values

Inclusion/Exclusion Criteria:

Inclusion criteria:

- A. Cirrhosis diagnosed by either of the following in a patient with chronic liver disease
 - a. Liver Biopsy
 - b. Radiologic evidence of varices, cirrhosis or portal hypertension
 - c. Laboratory evidence of platelet count <100,000 or AST/ALT ratio>1
 - d. Endoscopic evidence of varices or portal gastropathy
 - e. Fibroscan values suggestive of cirrhosis
- B. On treatment for hepatic encephalopathy (patient can be on lactulose and rifaximin)
- C. Age: at least 21 years of age
- D. Able to give written, informed consent (demonstrated by mini-mental status exam>25 at the time of consenting)
- E. Women of child bearing potential must agree to use effective contraception for the duration of the study and for 10 days prior and 30 days after the study
- F. Negative pregnancy test in women of childbearing age

Exclusion criteria:

- A. MELD score >22
- B. WBC count <1000 cells/mm3
- C. Platelet count < 25,000/mm3
- D. TIPS in place for less than a month
- E. Currently on antibiotics apart from rifaximin
- F. Infection at the time of the FMT (diagnosed by blood culture positivity, urinalysis, paracentesis as needed)

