Dosage: FMT Procedure #1 5 FMT capsules or 5 placebo capsules and 60 ml FMT enema vs 60 ml placebo FMT Procedure #2 5 FMT capsules or 5 placebo capsules

Route of Administration: Oral and enema for baseline, and oral only for Day 30

Timing of administration: Twice (at baseline and Day 30)

Procedures:

Once patients are randomized 1:1:1:1 into Group 1: Dual oral and rectal FMT, Group 2: Oral FMT and rectal placebo, Group 3: Oral placebo and Rectal FMT and Group 4: Oral and rectal placebo, both will be followed over 6 months with intensive follow-up in the first 30 days.

At the end of one month, we will provide another oral-route FMT or placebo to all subjects based on their initial assignment (Groups 1 and 2 will get oral FMT 5 capsules again, and Groups 3 and 4 will get 5 capsules of placebo again). All subjects will be followed with monthly visits till 6 months to assess SAEs.

An overview is shown below in Figure 1 (extended through 6 months)

Procedures:

Visit 1: After initial review of the medical record is completed and informed consent is obtained, potentially eligible patients will be interviewed and their questions about the study will be answered by the study team. Vital signs (including heart rate, blood pressure, respiratory rate, temperature) and weight will be measured. Physical exam will be performed. We will administer the Mini-mental status exam (MMSE)^{13 4}. For those <25, we will deem them not able to give consent and their clinicians will be notified. For the rest we will obtain blood and urine for further confirming eligibility (MELD score and complete blood count for platelet count/ANC). Patients will also be administered a safety test capsule orally to ensure they can swallow it without any issues. If the subject is eligible and can swallow the capsules and otherwise fits criteria, they will be randomized into one of the four groups (Groups 1-4, Table 2) and a date for visit 2 will be generated. A dietary recall will be performed and the patients will be asked to stay on the same diet throughout the trial. We will perform the validated lactulose/mannitol testing at baseline. Patients will undergo brain function tests and quality of life assessment during this visit to establish their baseline. Patients will be given a Stool Collection Kit to bring in the day of the baseline visit (Visit 2). They will also be given a symptom diary and instructions to complete it.

Table 2: Patient Groups

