Visit 4: All procedures as in visit 2 will be performed again, including dietary recall, targeted physical exam, and sample collection. All subjects will also get another oral FMT/placebo dose of 5 capsules each depending on their original assignment. All subjects in the study will get this intervention unless (a) they refuse the intervention (b) have undergone a liver transplant or have died/discharged to hospice (c) developed an infection or an SAE that was adjudicated to be related to FMT in the interim or (d) are currently undergoing antibiotic therapy for an infection that is not related to FMT.

For those who are infected due to an FMT-unrelated infection, we will approach the patients 2 days after the completion of the assigned antibiotic course. For those initiated on SBP (Spontaneous Bacterial Peritonitis) prophylaxis, we will provide the intervention after the initial SBP episode is treated. This may require delaying the intervention from day 30 to up to day 45 but this will still be counted as the second FMT.

All other subjects will be given the intervention and the blind will still be maintained. The brain function tests and QOL will be performed again. Groups 1 and 2 will get active FMT and groups 3 and 4 will get placebo FMT. No enemas will be given. The subjects will then be sent home.

Follow-up visits every month: The subjects will be followed monthly in person, or by phone or videoconference at Months 3, 4, 5 to evaluate dietary and medication changes and for safety analysis (hospitalizations, AEs or SAEs), targeted physical exam and for collection of samples at each study clinic visit. Mail-in kits for collection of stool, and urine will be provided along with instructions for use if visit is performed remotely. We will also perform the cognitive tests and QOL assessment at one month post-second intervention and at 6 months. We will continue to follow every patient for 6 months regardless of whether they developed an SAE or hospitalization in between. Only reasons not to follow them up for 6 months would be death, liver transplantation or patient withdrawal of consent.

End-of-Study visit: Per FDA mandates for FMT studies, we will see the patients at six months and we will evaluate AEs, interim hospitalizations, dietary recall, and perform targeted physical exam, QOL and brain function studies, and collect serum, and stool again. At this point the participation of the patient will end.

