3. The following will be recorded in all interventions (dose, Unit ID/Lot# of each treatment, Expiration Date and storage condition)

Number of interventions: One administration of rectal placebo or FMT and two administrations of oral FMT or placebo

We will ensure that each subject receiving active FMT will receive material (oral/rectal) from the same donor.

Duration of Follow-up after FMT: 6 months

Samples collected at baseline (before FMT), and at the visits specified above will be:

- a. Stool (microbiome, bile acid profile, metagenomics, metabolomics)
- Blood (CBC, Basic metabolic panel, LFTs, INR, endotoxin, and storage for circulating microbiome, systemic inflammatory markers, bile acids and metabolomics)
- c. Urine for metabolomics

Sample processing will be done using standard precautions at the McGuire VA Medical Center and samples will be stored for analysis of the secondary endpoints. Microbiota analysis will be performed at George Mason University and University of Minnesota, and metabolomics will be performed at the UC Davis NIH West Coast Metabolomics Center or Metabolon. We will perform the bile acid analysis at the McGuire VA Medical Center laboratories. Additional analyses at the Institute of Hepatology, London, UK, and the University of North Carolina at Chapel Hill. We may also use other referral laboratories as needed.

Statistical analysis: These will be performed using ANOVA of delta changes after intervention/follow-up using Chi-square and Fisher exact for non-parametric (hospitalizations, HE episodes, covert hepatic encephalopathy etc.), for continuous variables, and specialized bio-informatics analyses for the microbiota (see details below). These will be adjusted for age, gender, MELD score and alcoholic etiology of cirrhosis.

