- 1. Safety-related (at 6 months): Liver-related hospitalizations, other serious adverse events (SAE) and adverse events related to interventions.
- 2. Microbiota composition: Stool 16SrRNA sequencing and engraftment of donor into recipients.
- Inflammatory milieu: Endotoxemia (LAL), Systemic inflammatory cytokines (IL-6, TNF, IL-1b using ELISA)
- 4. Bile acid profile and gut-liver mediators expression: Bile acid profile using LC/MS in stool and serum and serum C4 (7α-Hydroxy-4-cholesten-3-one).
- 5. Urinary metabolomics to evaluate gut-microbial markers
- 6. Brain function: Two validated testing strategies, PHES and EncephalApp Stroop Test, and Quality of Life: Sickness Impact Profile (a validated profile for healthrelated quality of life in cirrhosis)

Adjudication: Data and safety monitoring for this study will be provided by the Clinical Science Research & Development (CSR&D) centralized Data Monitoring Committee (DMC). The DMC is provided by CSR&D to ensure independent oversight of the safety and integrity of the project. The DMC is an independent multidisciplinary group, whose members have collectively – through research, education, training, experience, and expertise – the requisite knowledge pertinent to the subject areas to be reviewed. Membership details are available on the CSRD website. The DMC will provide an ongoing independent evaluation of this study focused on safety and feasibility, including participant accrual and retention, adverse events monitoring, and data analyses. Meetings will be held three times per year at which recommendations will range from approval to continue (unconditionally or with conditions to be addressed) to probation or possibly termination, if there are problems with enrollment or safety concerns

All outcomes will be compared between groups as well as post-intervention to baseline.

Visits at VCU and VAMC:

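### Continuous secondary outcomes are analysed as change scores without the outcome's own baseline as a covariate, giving up precision that costs almost nothing to recover

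*Combined protocol and SAP*

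**What the plan says.** The Statistical analysis paragraph gives the method as "These will be performed using ANOVA of delta changes after intervention/follow-up" and then adds "These will be adjusted for age, gender, MELD score and alcoholic etiology of cirrhosis". The sentence between them is hard to parse, because the chi-square and Fisher tests run into a reference to continuous variables. Analysis of change is nevertheless the only method named there that suits a continuous outcome, the microbiota having its own bioinformatics plan. Neither ANCOVA nor adjustment for the outcome's baseline appears anywhere in the document.

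The baseline values are planned:

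- Cognition and quality of life, under Procedures, Visit 1: "Patients will undergo brain function tests and quality of life assessment during this visit to establish their baseline".
- Stool, blood and urine, in the sample list: "Samples collected at baseline (before FMT), and at the visits specified above will be".

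Cognition and quality of life are repeated at Visit 4, and the follow-up paragraph adds: "We will also perform the cognitive tests and QOL assessment at one month post-second intervention and at 6 months". The third secondary aim is "To evaluate changes in systemic inflammatory cytokines and endotoxin, quality of life and cognitive function compared to pre-FMT baseline and compared to placebo", and Endpoints and Plan of Analysis states: "All outcomes will be compared between groups as well as post-intervention to baseline".

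**The concern.** A change score subtracts the whole baseline value, which fixes the slope of follow-up on baseline at 1. ANCOVA estimates that slope. Unless the true slope is close to 1, the change score carries avoidable baseline noise into every between-group comparison. The four planned covariates do not replace a patient's own starting PHES, Stroop time, SIP score or cytokine level.

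The outcomes affected are PHES, EncephalApp Stroop, SIP, endotoxin, cytokines, and bile acid and metabolite measures. Brain function and quality of life are also named in the overall objective. No SD, effect size or power is given for any of these outcomes. The 25 patients per group come from hospitalization rates alone, so the pairwise comparisons of continuous outcomes have no planned margin. The choice has to be made in advance: picking between change-score and baseline-adjusted results after seeing both would not be credible.

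**Working it through.** **The plan's own figure.** The Sample size paragraph states power of 94%, 98% and 100% at 15, 20 and 25 per group, for hospitalization. A four-group chi-square test (3 df, alpha 0.05) with the assumed rates of 80%, 30%, 30% and 10% gives 94.9%, 98.8% and 99.8%. This is a binary calculation and the present point does not alter it. There is no stated figure for a continuous outcome to reproduce.

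**Inputs.** From the plan: 100 patients, four groups of 25, four covariates, alpha 0.05. Two-sided testing is assumed because the plan does not state it. Residual df are 100 − 4 − 4 = 92 for change, and 91 with the baseline added. The correlation rho (baseline to follow-up, after the four covariates) is not in the documents and is taken over a range.

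**Variance, equal SDs.** With outcome variance 1:

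- change score: 2(1 − rho)
- ANCOVA: 1 − rho²
- ratio: (1 − rho²) / [2(1 − rho)] = (1 + rho)/2

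The net ratio in the table comes from a simulation of 20,000 trials (100 patients, four groups, four null covariates) and includes the cost of the extra parameter. The detectable difference is for 25 vs 25 at 80% power, in outcome SDs, with the ANCOVA variance inflated by 1 + 1/90.

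| rho | (1+rho)/2 | net ratio | detectable, change | detectable, ANCOVA | fall |
|---|---|---|---|---|---|
| 0.3 | 0.65 | 0.659 | 0.948 | 0.768 | 19% |
| 0.5 | 0.75 | 0.763 | 0.801 | 0.697 | 13% |
| 0.7 | 0.85 | 0.858 | 0.620 | 0.575 | 7% |
| 0.9 | 0.95 | 0.963 | 0.358 | 0.351 | 2% |

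Both estimators were unbiased in the simulation (means 0.597 to 0.603 for a true 0.60). Break-even with equal SDs is where (1+rho)/2 × (1 + 1/90) = 1, that is rho ≈ 0.98.

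**When a planned covariate is related to the baseline.** A separate simulation (3,000 trials per setting) let one covariate correlate 0.3 with the outcome's baseline. The variance ratios at rho 0.3, 0.5, 0.7 and 0.9 were 0.69, 0.79, 0.88 and 0.97, against 0.64, 0.74, 0.87 and 0.96 with no such correlation. The gain shrinks slightly but remains.

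**What the documents suggest about rho.** The only source is MELD in the earlier enema trial (10 per group). Baseline SDs are 3.7 (no FMT) and 2.9 (FMT). In the row "Day 0 minus day 35" the SDs of change are 2.4 and 1.7. With equal SDs, rho = 1 − SD_change² / (2 × SD_base²):

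- no FMT, day 35: 1 − 5.76/27.38 = 0.79
- FMT, day 35: 1 − 2.89/16.82 = 0.83
- days 6 and 12, no FMT (SDs of change 1.4 and 1.3): 0.93 and 0.94
- days 6 and 12, FMT (SDs of change 1.4 and 1.3): 0.88 and 0.90

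The variance gain is (1 − rho)/2: 3.1% to 10.5% overall, and 10.5% and 8.6% at day 35, the interval nearest Visit 4. The detectable difference goes from 0.519 to 0.494 at rho 0.79 (5% lower) and from 0.277 to 0.275 at rho 0.94 (1% lower).

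**Unequal SDs at day 35.** Let follow-up SD = k × baseline SD and d = SD_change/SD_base. The slope is (1 + k² − d²)/2 and the gain is (1 − slope)²/d². With d² = 5.76/13.69 = 0.421 (no FMT) and 2.89/8.41 = 0.344 (FMT):

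- k = 0.9: gain 22.2% and 20.7%
- k = 1.1: gain 2.6% and 1.3% (1.6% and 0.2% after the degree of freedom)
- k = 1.15: slopes 0.951 and 0.989; net loss 0.5% and 1.1%

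**The case against.** The strongest reply is that nothing here is wrong. Change-score analysis is valid, the outcomes are secondary, and the trial's primary aim is safety and tolerability. The larger gains rest on assumed correlations. The only figures in the documents give at most about 11% less variance, and MELD is a weak guide to cognition, quality of life or cytokines. The pilot correlations are also not adjusted for the four covariates, whereas rho above is. The addition is not strictly free either: it uses a degree of freedom, and if the follow-up SD were about 15% above baseline the gain would disappear even at a correlation of 0.83 to 0.86. Finally, the statistical paragraph is brief and does not say that its covariate list is exhaustive.

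Most of this stands as a limit on size. The gain for the actual endpoints is unknown and may be small. It does not make the change unwise, because the worst case examined is a loss of about 1% in variance, against a possible gain many times larger. Nor does the brevity of the paragraph help: a list that omits the outcome's baseline leaves the model to be chosen later.

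**Conclusion.** The concern holds as a recommended improvement, not a required correction. The planned analysis is unbiased but less precise than it could be whenever the slope of follow-up on baseline is not close to 1. Over an assumed rho of 0.3 to 0.9 with equal SDs, the variance falls by 35% to 5% (34% to 4% net of the extra parameter) and the detectable difference by 19% to 2%. Pilot MELD suggests the small end, a 1% to 5% fall in detectable difference, but it is not an efficacy endpoint here and stops at day 35. The documents contain nothing on rho for the affected outcomes or for the later assessments. The primary endpoint, the hospitalization power and the separate microbiota plan are untouched.

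**What to change.** For continuous outcomes, specify an ANCOVA of the follow-up value on the four-level group factor, with the outcome's own baseline and the four covariates already listed, at each planned follow-up assessment. Results can still be reported as change: using the change score as the response with baseline as a covariate gives identical group differences. State that MELD as a covariate means its baseline value.

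Two clarifications belong in the same edit:

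- Reconcile the assessment times. The Brain function paragraph equates Visit 4 with one month after the second FMT, while Procedures gives the second dose at Visit 4 and the Quality of Life paragraph lists the two times separately.
- Say whether the covariate adjustment applies to the binary outcomes. If it does not, say that the chi-square and Fisher results are unadjusted.

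The cost is one residual degree of freedom (92 to 91 with 100 patients) and SAP wording fixed before unblinding. No new data or visits are needed.

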Sample size: Based on the published study with rectal FMT¹⁰, we found that standard of care patients had an 80% chance of hospitalization at 6 months, while FMT had a 20% hospitalization rate. Given that we had used antibiotics for this study, we will assume that rectal FMT alone will have a 30% chance of hospitalization rate without antibiotics. We will also assume that oral FMT alone will have a similar hospitalization rate, and their combination will have a 10% hospitalization rate. Using a significance level of α =0.05, a sample size of 25 per group will provide a power of 100% between groups, 20 per group will give a power of 98% to define differences between the groups, while a sample size of 15 patients per group will give a power of 94% between the groups. Therefore, we will enroll 100 patients (25 in each group) for this trial. This sample size calculation will also be valid when we include the second oral FMT with a sample of 10 per group giving 88% power, 15 per group giving 97% power and 25 giving 99% power.

Specialized analyses:

Inflammatory milieu: We will perform the analysis for endotoxemia using the validated Limulus amebocyte lysate (LAL) assay and serum inflammatory cytokines (IL-6, TNF, IL-1b) using ELISA at [name] and [name]'s laboratory at the McGuire VAMC or at Assaygate¹⁴.

Microbial Analysis: Bacterial community composition in stool will be characterized using OTU counts generated as described above. OTU counts will be converted to measures of relative abundance to account for variation in sequencing coverage between samples and compared to the donor sequence. Statistical analysis will be carried out using the statistical software package R. Alpha (α) diversity (richness and evenness of taxa within a population) will be reported using the Shannon Index¹⁵ and Chao1 richness estimator¹⁶. Changes in abundance of individual taxa will also be analyzed using traditional univariate statistical methods. We will use LEfSe (Linear discriminant analysis Effect Size) to determine the features most likely to explain differences. All comparisons will be performed between treatment arms, to gauge donor engraftment in the three FMT-assigned arms, as well as within groups to compare to their baseline microbial composition¹⁷. These will be performed at George Mason University and University of Minnesota. Functional analysis using bile acids, SCFA and metabolomics will also be performed.

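### The plan fixes neither the scale nor a baseline adjustment for the assay endpoints; read naturally, its ANOVA of change would be inefficient if cytokines, endotoxin, C4 and bile acid concentrations are right-skewed

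*Combined protocol and SAP*

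**What the plan says.** The Statistical analysis paragraph opens with the general method: "These will be performed using ANOVA of delta changes after intervention/follow-up". It then names chi-square and Fisher tests for outcomes such as hospitalizations and HE episodes, and bioinformatic methods for the microbiota. It closes with the covariates: "These will be adjusted for age, gender, MELD score and alcoholic etiology of cirrhosis". The baseline value of the outcome is not among them.

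The assays are secondary endpoints 3 and 4 under Endpoints and Plan of Analysis: "Endotoxemia (LAL), Systemic inflammatory cytokines (IL-6, TNF, IL-1b using ELISA" and "Bile acid profile using LC/MS in stool and serum and serum C4". Under Specialized analyses, the Inflammatory milieu entry says how endotoxin and cytokines are measured but not how they are analysed. The Microbial Analysis entry adds "Functional analysis using bile acids, SCFA and metabolomics will also be performed", again without a method.

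The document contains no log or other transformation for these assays, no rank-based alternative, no rule for values below a detection limit, and no mean, SD or expected effect for any of them.

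**The concern.** Immunoassay and mass-spectrometry concentrations cannot be negative. If their spread grows with their level, and treatment lowers each patient by a similar percentage, the absolute change is large in patients who start high and small in the rest. An ANOVA of absolute change then gives most of its weight to a handful of patients, and a real proportional fall is easy to miss.

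Secondary aim 3 and secondary endpoints 3 and 4 rest on these assays, and the overall objective names systemic inflammation and bile acid composition. There are 25 patients per arm, and the only power statement concerns hospitalization. What is at stake is missed effects and fragile estimates. There is also an open choice of scale across several assays that could be made after the data are seen.

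**Working it through.** **1. The plan's own power figures.** The Sample size paragraph gives 94%, 98% and 100% for 15, 20 and 25 per group. With rates of 80/30/30/10% the mean is 0.375. The squared deviations sum to 0.1806 + 0.0056 + 0.0056 + 0.0756 = 0.2675. For a four-group chi-square test (3 df, α = 0.05) the noncentrality is λ = n × 0.2675 / (0.375 × 0.625) = 1.141n, or 17.1, 22.8 and 28.5. Power is 94.9%, 98.8% and 99.8%, so the figures reproduce. They are overall tests of hospitalization and carry no information about the assays.

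**2. Which scale is meant.** The text says delta and stops there. In the account of the team's enema trial, MELD and white-cell results are tabulated as simple differences between day 0 and a later day. That makes the measured scale the natural reading, but it remains an inference.

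**3. Mechanism.** Let Y0 be baseline and Y1 = r × Y0 × e, with r the treatment ratio and e random error. Then Y1 − Y0 = (r × e − 1) × Y0, which scales with Y0. On the log scale, log Y1 − log Y0 = log r + log e, which does not.

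**4. Assumed inputs; none is in the documents.** Two arms of 25, two-sided α = 0.05, log-normal baseline and follow-up, log-scale correlation 0.6, r = 0.55 (a 45% fall), log-SD σ = 0.6, 0.8 or 1.0. Simulated power, good to about a point:

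| Analysis | σ = 0.6 | σ = 0.8 | σ = 1.0 |
|---|---|---|---|
| Raw change | 80% | 50% | 31% |
| Raw ANCOVA on baseline | 96% | 74% | 48% |
| Log change | 97% | 83% | 64% |
| Log ANCOVA on log baseline | 99% | 89% | 73% |

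Hand check of the log rows. The effect is |ln 0.55| = 0.598. The SD of log change is σ√(2(1 − 0.6)) = 0.894σ. The ANCOVA residual SD is σ√(1 − 0.36) = 0.8σ. The standard error is SD × √(2/25). At σ = 0.8 for log change, SD = 0.716 and SE = 0.202, so 0.598/0.202 = 2.95; less the critical value 2.01 this is 0.94, giving power of about 83%. For log ANCOVA, SD = 0.64 and SE = 0.181, so 3.30 − 2.01 = 1.29, about 90%. Both agree with the simulation.

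**5. How few patients drive it.** In a neighbouring setting (r = 0.6, σ = 0.8 to 1.0), the 3 most extreme of 50 patients (6%) carry about 54 to 62% of the within-group sum of squares of raw change. Even normal data put more than 6% there, so this is a description and not a test.

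**6. How far the answer moves with the assumptions.**
- 45% fall, σ = 0.3 to 0.4: gap of 0 to 1 point, since both analyses reach 99 to 100%.
- 20% fall, σ = 0.6/0.8/1.0: raw 23/13/8%, log 31/19/13%. The gap is 5 to 8 points and neither is adequate.
- Additive effect: 68 to 69% on both scales, so no gain.
- 45% fall with 40% of baseline values below the detection limit, set to half the limit: the gain of log change over raw change is 11/18/18 points.
- Four-arm F test with ratios 1/0.7/0.7/0.5 and σ from 0.3 to 1.2: gap of 0 to 46 points.
- Type I error: 3.8 to 4.8% on raw change, about 5% on log change.

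**7. Scale and baseline contribute separately.** At r = 0.6 and σ = 0.8, raw change gives 40%, raw ANCOVA 62%, log change 70% and log ANCOVA 78%. Baseline adjustment alone recovers about 21 of the 29 points between raw and log change. With 40% undetectable and a 45% fall, raw ANCOVA (91/67/45%) equals or beats unadjusted log change (78/60/45%).

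**The case against.** The strongest reply is that the document never says raw. A delta of log values fits the sentence, which is visibly garbled and names none of these assays. That stands: a reader might infer that the plan commits to untransformed differences, but the text shows only that no scale is specified.

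A reader might also take the gap of roughly 17 to 33 points between the raw and log rows of the table as a property of this trial. It is not. It follows wholly from assumed skewness, correlation and effect, and other plausible inputs give anything from 0 to 46 points.

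Nor is a log scale costless. It changes the estimand to a ratio of geometric means, and zeros and undetectable values need a rule, which reduces the gain. Taking logs without baseline adjustment is also not the best available analysis.

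A log for every assay would go too far. The team's earlier work describes bile acids as a "decrease in proportions of fecal secondary BAs, conjugated BAs and increase in sulfated BAs". Proportions are bounded and may be zero. Because bile acids also appear under Specialized analyses, it is unclear whether the ANOVA sentence is meant to govern them.

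Finally, these are secondary mechanistic endpoints and type I error is not inflated. That limits the importance of the point but does not remove it: no scale, baseline adjustment or detection-limit rule is written anywhere, and a better analysis can be named now at very little cost.

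**Conclusion.** The point holds as a gap in pre-specification with a clearly better alternative. The plan names ANOVA of change, states no scale and omits the outcome's baseline from its covariates. If the concentration-type assays are right-skewed with roughly proportional effects, the natural reading of that method is dominated by a few patients and loses power. Under the stated assumptions the loss against log ANCOVA is about 19, 39 and 42 points (99 − 80, 89 − 50, 73 − 31), part of it due to scale and part to the missing baseline. The documents supply no data to say where in the range this trial falls. They do not support a fixed loss, a claim that raw differences are mandated, or a claim that false-positive risk rises. The primary endpoint and the sample size are untouched. The change is worth making, but it is not critical to the trial.

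**What to change.** Before unblinding, add a short paragraph for secondary endpoints 3 and 4:
- Log-transform IL-6, TNF, IL-1b, endotoxin, C4 and bile acid concentrations.
- Compare groups by ANCOVA on the log follow-up value, adding the log baseline to the four covariates already listed.
- Report geometric mean ratios with 95% CI.
- State one rule for values below the detection limit, and give a rank-based analysis as sensitivity.
- Name a method suited to proportions for bile acid proportions, and say whether this paragraph or the specialized analyses govern bile acids.
- Leave PHES, EncephalApp Stroop and SIP on their own scales.

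The cost is a few sentences of text, with no change to patients, visits or samples. There are two drawbacks: results are read as ratios of geometric means and not as mean differences, and they depend to some extent on the detection-limit rule.
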